**Proposed schedule:**

Start of trial period Phase I study	01.01.2021
End of trial period Phase I study	31.05.2021
Start of trial period Phase II study	01.06.2021
End of trial period Phase II study	01.03.2022

## Abbreviations

16S rRNA (16S ribosomal ribonucleic acid), 12	IBD (Inflammatory bowel disease), 11
AE (adverse event), 21	ICMJE (International Committee of Medical Journal Editors), 36
APC (Antigen-presenting cells), 11	IPAA (restorative ileal pouch anal anastomosis), 10
ATC classification (Anatomical Therapeutic Chemical classification), 24	IPEC-J2 cells (Intestinal porcine enterocyte J2 cell line), 15
BMI (body mass index), 27	IUPAC (International Union of Pure and Applied Chemistry), 14
CD (Crohn's disease), 11	JAK/STAT (Janus kinase/signal transducer and activation of transcription), 13
cDNA (complementary deoxyribonucleic acid), 24	MAPK (mitogen-activated protein kinase), 13
CLR (C-type lectin receptor), 11	MRSA (Methicillin-resistant Staphylococcus aureus ), 14
CPR (Civil Person Registry), 33	PDAI (Pouchitis Disease Activity Index), 10
CRFs (Case report forms), 22	PERMANOVA (permutational analysis of variance), 31
DC (Dendritic cells), 11	PI-3 (phosphatidylinositol 3), 13
ESBL (extended-spectrum $\beta$ -lactamase-producing E. coli ), 14	PRR (pattern recognition receptors), 11
EUDRACT database (European Union Drug Regulating Authorities Clinical Trials database), 36	rhGM-CSF (recombinant human granulocyte-macrophage colony-stimulating factor), 24
FAP (Familiar adenomatous polyposis), 10	s.c. (subcutaneous), 17
FFP (formalin fixed paraffin), 28	SAE (Serious adverse events), 30
GCP unit (Good clinical practice unit), 26	SAR (Serious adverse reactions), 30
GDPR (General Data Protection Regulation), 32	SUSAR (Suspected unexpected serious adverse reaction), 30
GM-CSF (granulocyte-macrophage colony stimulating factor), 13	TLR-5 (Toll-like-receptor 5), 13
GMP (Good Manufacturing Practice), 24	UC (Ulcerative colitis), 10
HE (hematoxylin/eosin), 28	
i.m. (intramuscular), 17	
i.v. (intravenous), 17	

## 1. Summary

A definitive cure for patients with treatment-refractory ulcerative colitis is proctocolectomy with IPAA (restorative ileal pouch anal anastomosis) (1). Up to 50% of all patients develop “pouchitis” within the first five years after surgery, an inflammatory condition that is as yet poorly understood and without official consensus on treatment (2). Treatment modalities include oral antibiotics as well as immunomodulators, steroids, probiotics and biological agents, but up to 20% of these patients develop chronic, treatment-resistant pouchitis, which can result in pouch failure and the need for reoperation with the possible creation of an ileostomy (11,12).

The etiology of pouchitis is thought to be similar to other inflammatory bowel diseases, in that genetic and bacterial factors, a compromised gastrointestinal barrier and immunological components seem to play a role. Its pathogenetic mechanisms seem to mimic Crohn’s disease, in which smaller studies have shown some effect of systemically administered GM-CSF (granulocyte-macrophage colony stimulating factor) on the gut macrophage function in clearing microorganisms and maintaining the mucosal barrier (3–6).

We hypothesize that GM-CSF will have an effect in the treatment of pouchitis because of its similarity to that of Crohn’s disease. In order to maximize effect on the inflamed mucosa and minimize systemic side effects, we intend to administer it locally in the pouch. In a safety and proof-of-concept intervention study we will combine 50 µg GM-CSF with two well-known antibiotics, 400 mg Fosfomycin and 100 mg metronidazole, to target both the suspected immunological as well as the bacterial role in the pathogenesis of pouchitis.

The effect on the pouch will be assessed endoscopically and histologically by taking biopsies that will also be examined for changes in the microbiome. Patients will be clinically examined and have blood samples taken to monitor for adverse reactions. The primary outcome measure will be an assessment of adverse reactions and tolerability of the drug. Secondary outcome measures will be a change in the pouchitis disease activity index (PDAI), a change in the microbial diversity, and a change in inflammatory markers.

This study is based on a non-randomized trial design with an open-label single group assignment.

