#### Phase I – Safety study

##### Primary outcome measure

- Safety: Determine serious adverse reactions or adverse reactions from the application of GM-CSF, metronidazole and fosfomycin in the pouch as seen in Appendix 8. The category of the reactions will be determined by the principal investigator according to the safety assessment described in chapter 7.  
A summary of the product characteristics of GM-CSF, fosfomycin and metronidazole will function as a reference document in evaluation of adverse effects. We will monitor adverse reactions from the day of the intervention in Phase I and II until respectively day 30 and 37. The safety of the intervention will be measured by adverse reactions.

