## Phase II – Proof of concept study

### Primary outcome measure

- Change in the pouchitis disease activity index (PDAI) – A decrease of 3 points or more will be determined as an improvement in PDAI from before application of the study drug to 7 days after application of the study drug

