## 8. Statistical considerations

We plan to include 6 patients in the Phase I study to test tolerability, and 12 patients in the Phase II study to test effectiveness of the treatment. The trial will end with the last visit of the last patient (Day 37 of the last patient). This is a safety and clinical proof-of concept intervention study, and we are, to the best of our knowledge, the first group to look into local treatment with GM-CSF and antibiotics of biofilm in patients with pouchitis after IPAA for ulcerative colitis. We expect this number of patients to be sufficient to provide the necessary experience in implementing the technique and form a basis for future studies, including future sample size calculation. This is based on calculations on number of patients required to achieve statistical significance of paired before-and-after comparisons by non-parametric tests. To achieve statistical significance at 1% level in Phase II, 9 patients are needed. As there is a risk of patients withdrawing from the trial prematurely or not receiving all interventions, we aim to include 3 additional patients.

Our primary objective is to test for adverse events or reactions in Phase I and a significant change in PDAI in Phase II, defined by a decrease of 3 points. Differences pre- and post-treatment will be described by means and standard deviations, or median and range when appropriate, and will be analyzed by the appropriate statistical tests. All patients described in chapter 5 as 'Completed test persons' will be included in the statistical analysis.

Microbial diversity changes will be analyzed using PERMANOVA (permutational analysis of variance). Other secondary objectives like change in WBC and CRP will be analyzed using the appropriate statistical tests.

Data will be analyzed using non-parametric or parametric statistics depending on the distribution of the data. P-values  $\leq 0.05$  are considered significant. Correction for multiple comparisons will be performed if needed. Descriptive statistics will be used for baseline characteristics.

Missing data will be handled depending on the type of data missing. If missing data results in a patient not being able to be defined as a 'Completed test person' (Chapter 5), the patient is excluded from the trial and a new patient will be recruited. If individual results are missing (e.g. laboratory values), the last known values will be used for analysis.

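### For Phase II the Summary reverses the primary and secondary outcomes of sections 3 and 8, and the Phase I safety outcome is adverse reactions in section 3 but adverse events or reactions in section 8

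*Protocol*

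**What the plan says.** **Summary (section 1).** The work is described as one study: "In a safety and proof-of-concept intervention study we will combine 50 µg GM-CSF with two well-known antibiotics". One outcome list follows. On the primary outcome: "The primary outcome measure will be an assessment of adverse reactions and tolerability of the drug". On the rest: "Secondary outcome measures will be a change in the pouchitis disease activity index (PDAI), a change in the microbial diversity", followed by inflammatory markers. No phase is named, and the Phase I and Phase II paragraphs of the Summary give no outcomes of their own.

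**Section 3, Phase I.** The primary outcome is "Safety: Determine serious adverse reactions or adverse reactions from the application of GM-CSF, metronidazole and fosfomycin in the pouch as seen in Appendix 8", and "The safety of the intervention will be measured by adverse reactions". PDAI change is secondary.

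**Section 3, Phase II.** PDAI change stands under the primary heading: "A decrease of 3 points or more will be determined as an improvement in PDAI". The same sentence also appears in both lists of secondary outcomes, so the heading, not the sentence, gives it primary status. Safety is listed as secondary.

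**Section 8.** "Our primary objective is to test for adverse events or reactions in Phase I and a significant change in PDAI in Phase II".

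**The concern.** There are two separate inconsistencies.

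For Phase II, a reader of the Summary takes safety as primary and PDAI as secondary, while a reader of section 3 takes the opposite. The protocol does not say which section prevails. In an open-label, single-arm trial a fixed primary outcome is one of the few guards against selective emphasis. Section 10 (General considerations) says the trial will be entered in a public registry, so the Summary's version could be carried over into that entry.

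For Phase I, the primary safety measure changes from reactions to events or reactions between sections 3 and 8. If the narrower term is used, events the protocol itself treats as known drug effects drop out of the headline safety result.

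**Working it through.** **1. Phase II outcomes side by side**

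| Place | PDAI change | Safety |
|---|---|---|
| Summary (no phase named) | secondary | primary |
| Section 3, Phase II | primary | secondary |
| Section 8 | primary objective | not named for Phase II |

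Sections 3 and 8 agree on PDAI. The Summary disagrees with both. For Phase I the Summary agrees with section 3, apart from adding tolerability.

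**2. Which text does the sample size support?**

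Inputs from section 8: 9 Phase II patients for significance at the 1% level, based on paired before-and-after comparisons with non-parametric tests, plus 3 for withdrawals. No power, effect size, standard deviation or sidedness is given, so the only possible check is whether the level can be reached at all.

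For an exact sign or signed-rank test the smallest two-sided p-value with n pairs is 2/2^n:

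- n = 7: 2/128 = 0.0156
- n = 8: 2/256 = 0.0078
- n = 9: 2/512 = 0.0039

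The one-sided minimum is 1/2^n, which is 1/128 = 0.0078 at n = 7. So 8 patients (two-sided) or 7 (one-sided) are the fewest that can reach 1%. With 9, the two-sided signed-rank test still reaches it when only the smallest change goes the wrong way: 2 × 2/512 = 0.0078. At n = 8 that case gives 2 × 2/256 = 0.0156. The stated 9 is consistent with this reading, and 9 + 3 = 12.

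PDAI is scored before and after treatment. An adverse-reaction count has no baseline value to pair with. Of the two candidates for Phase II primary, the calculation fits only PDAI.

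**3. Events against reactions in Phase I**

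- Section 7 defines an adverse event without regard to cause. It defines an adverse reaction as an event with a reasonable possibility of being caused by the study drug. Reactions are therefore a subset of events.
- Section 3 lists, for each drug, known effects that are not to be registered as adverse reactions. Counting nausea and vomiting separately, GM-CSF has 20. Metronidazole adds 6 not already listed (glossitis, dry mouth, dysgeusia, stomatitis, candida superinfection, dark urine). Fosfomycin adds 5 more (phlebitis, decreased appetite, vertigo, headache, fatigue). The total is 20 + 6 + 5 = 31 distinct effects. They include fever, abdominal pain, diarrhea, hypotension and cardiac dysrhythmia.
- A patient with one of these as a non-serious event is counted under section 8's wording but not under section 3's.
- Appendix 8 already has a tick box for each of the 31, in a side-effects block separate from the adverse-reactions field. Section 7 also requires all adverse events to be recorded. The data for the wider count will exist.

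**The case against.** The strongest reply on Phase II is that the Summary is abridged: it carries the Phase I list and omits the split, and it never says the list covers both phases. Sections 3 and 8 agree, and the sample size fits them. This stands. A reader might infer that the Phase II primary outcome is open and could be chosen after the data are seen, or that the protocol gives three rival primary outcomes. The documents do not support either reading. Phase II has two versions, and one of them is backed by the objectives, the statistics section and the sample-size basis.

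On Phase I, section 8 speaks of an objective, not an outcome measure, and may simply be loose wording. All events are recorded in any case. That is fair, but it does not settle which set the primary result reports.

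A reader might also infer that the whole Phase I result hangs on the unblinded investigator's view of cause, because "The category of the reactions will be determined by the principal investigator according to the safety assessment described in chapter 7". That goes too far:

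- Section 7 treats every serious adverse event as related to the study drug.
- Section 4 makes the start of Phase II depend on serious events or reactions.
- Although section 7 also mentions a six-level causality scale as an option, it gives a working related/not-related rule.
- The 31 listed effects are left out by rule, not by judgement.

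Nor can the effect be stated as a shift in a proportion of the 6 patients, because the protocol sets no Phase I proportion, threshold or test.

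**Conclusion.** The point holds in two limited parts.

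First, the Summary contradicts sections 3 and 8 on the Phase II primary outcome, with PDAI and safety in reversed order. The intended answer, PDAI, can be recovered from the rest of the protocol. The fault is a wrong statement in the Summary, and no patient number changes. That the Summary's list covers Phase II is an inference from its undivided wording.

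Second, the Phase I primary safety outcome uses two terms that the protocol defines differently. The gap matters for non-serious events, where 31 listed effects can be missing from a count of reactions. How many patients this would affect cannot be derived from the protocol. The direction is clear: a count limited to reactions can only be equal to or lower than a count of events.

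**What to change.** - Rewrite the Summary by phase to match section 3: Phase I primary is safety; Phase II primary is PDAI change, with safety secondary.
- Use one safety term in section 3 (Phase I primary outcome) and section 8.
- Report the Phase I primary as the number of patients with any adverse event and the number with any serious adverse event, including the known effects listed in section 3 and Appendix 8. Show adverse reactions as a subset. Choosing events over reactions goes a step beyond reconciling the wording; the reason is that it avoids a falsely clean safety result.
- Use the same wording in the registry entry.

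The cost is protocol wording and a safety table that is slightly longer and less favourable. No new data, visits or patients are needed.

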### Phase I

The tolerability of treatment will be tested on 6 patients with pouchitis with a single dose of the combined medication applied endoscopically in the pouch. Endoscopy with the taking of biopsies will be performed before and one week after administration of the medication, as well as blood samples before and after the medication. After the follow-up endoscopy, the patient will receive standard oral metronidazole or ciprofloxacin treatment for 10 days.

### Phase II

Depending on effect of the first study, the second study plans for the treatment of 12 patients. Endoscopy with biopsies will be conducted with the first application of the study drug combination in the pouch, and afterward a daily dosage for another 6 days. Clinical and endoscopic control after 14 days with blood samples and biopsies will be done. After the follow-up endoscopy, the patient will receive standard oral metronidazole or ciprofloxacin treatment for 10 days.

## Inclusion criteria

### Patients

- Of any gender
- Over 18 years of age
- Have a previous diagnosis of ulcerative colitis
- Have had IPAA surgery, and
- Have been diagnosed with pouchitis
- Be able to understand and complete study procedures as determined by the investigator
- Be able to speak either Danish or English
- Be able to comply with study procedures for the length of the study
- Use a highly effective contraception method for the duration of the trial (until day 30 in Phase I and until day 37 in Phase II), such as implants, injectables, oral contraceptives, IUD (intrauterine device), sexual abstinence or vasectomized partner.

Written informed consent must be obtained.

### Exclusion criteria

- Patients with a previous allergic reaction to GM-CSF, metronidazole or fosfomycin
- Patients who are currently under antibiotic treatment or have received antibiotic treatment within the past 30 days
- Patients currently pregnant or breastfeeding
- Patients with ASA IV classification (American Society of Anesthesiologists physical status classification)
- Patients with severe pulmonary disease
- Patients with autoimmune thrombocytopenia
- Patients with severe renal impairment (eGFR < 40 ml/min)
- Patients with alcohol use disorder or history of drug abuse
- Patients currently in treatment for any malignant or hematological disease
- Patients with a previous history of cancer will be excluded from the study (except for patients with well-treated and stabile cancer after a control period of more than two years).
- Patients with anticipated compliance problems as determined by the investigator

Patients can voluntarily withdraw from participation in this study at any time as well as withdraw from receiving the study intervention for any reason. The investigator can withdraw patients if the investigator feels the safety of the patient is compromised by participating in the study.

Adverse events and reactions will be monitored and followed up until the end of the study and/or resolution of the adverse event or reaction or until the adverse event or reaction is considered chronic.

In accordance with Danish law on personal data, we have approval for this trial from Region Sjælland (REG-106-2020) through their data application system. Data handling will be in accordance with the act on processing of sensitive personal information, the GDPR (General Data Protection Regulation) and the Data Protection Act. We have received conditional approval for the trial from The Research Ethics Committee (Application no: 75784) and the Danish Medicines Agency (EudraCT: 2020-000609-10).

The study will be conducted in the Surgical Department of Zealand University Hospital in cooperation with the Department of Gastroenterology and Hepatology of Zealand University Hospital. It will contribute to knowledge of the pathogenesis of pouchitis and whether a combination of GM-CSF and antibiotics given locally has an influence on the inflammation of the mucosa.

Following completion of the study, the positive, negative or inconclusive results of this research will be published in an international peer-reviewed scientific journal.

## 2. Background and scientific rationale

The surgical procedure of choice for patients with therapy-resistant UC (ulcerative colitis) is proctocolectomy with IPAA (ileal pouch anal anastomosis) (1). The intent of the procedure is a definitive cure of the disease and reduction of the risk of developing malignancy while preserving continence.

Pouchitis, inflammation of the mucosa of the ileoanal reservoir, is one of the most common complications after IPAA. (2) Symptoms of pouchitis include hematochezia, increased stool frequency and urgency, abdominal cramping, pain, nausea, incontinence and fever, as well as extraintestinal manifestations. Endoscopy typically shows the mucosa to be erythematous, with friability and loss of vascular patterns. Histology shows signs of inflammation and extravasation of red blood cells in the lamina propria. Interestingly, the incidence of pouchitis is about 10 times lower in patients after IPAA in FAP (Familial adenomatous polyposis) (7). Various scoring systems have been developed to assess the severity of inflammation in pouchitis, of which the PDAI (Pouchitis Disease Activity Index) is the most common. It assesses clinical, endoscopic and histological features (8) (see Table 1 in Appendix 1).

Pouchitis can be further categorized into acute and chronic pouchitis.

- Acute pouchitis – duration <4 weeks
- Chronic pouchitis – duration >4 weeks despite therapy

The incidence of acute pouchitis has been reported to be up to 50% at 5 years and there is no official consensus on treatment (9,10).

Treatment includes oral antibiotics, most often with metronidazole and/or ciprofloxacin. The standard treatment at Zealand University Hospital for acute pouchitis consists of a 10-day treatment period with oral metronidazole or ciprofloxacin. Metronidazole, while effective, can cause nerve damage after prolonged use in high doses. As patients often experience repeated flare-ups of acute pouchitis or chronic pouchitis, this risk increases due to repeated and lengthy use (11).

Other treatment modalities include probiotics, immunomodulators, steroids and biological agents (12,13). Up to 20% of patients with acute pouchitis can develop chronic pouchitis or chronic refractory pouchitis (14). While these can also be manageable with medical treatment, a small percentage of patients develop therapy-resistant pouchitis. A meta-analysis in 2017 by Segal et al. suggested that, on average, remission can be achieved in up to 59% of patients, but that chronic pouchitis still is challenging because the pathogenesis behind it is not fully understood (15). In therapy-resistant pouchitis, surgery with fecal diversion with the construction of an ileostomy is the treatment of choice and this results in the loss of anal defecation. Pouch failure ranges between 3.5% after 5.5 years to up to 9% after 10 years in various studies (16,17).

## Introduction

### Pathogenesis of pouchitis and inflammatory bowel disease

The pathophysiology of pouchitis after IPAA is poorly understood. Controversy exists as to whether pouchitis is a remanifestation of ulcerative colitis that mimics CD (Crohn's disease) or a type of Crohn's disease of the pouch. Just as in IBD (Inflammatory bowel disease), its etiology is thought to be multifactorial involving genetic and environmental factors including bacterial, mucosal barrier and immunological components (2,18).

There are several similarities between Crohn's disease and pouchitis, which questions its origin as a simple reactivation of ulcerative colitis in the mucosa of the ileum with colonic metaplasia:

- Pouchitis often responds to antibiotic treatment. Ulcerative colitis generally does not respond to antibiotics, whereas Crohn's disease does (19).
- Fistulas, which can appear in pouchitis, are often associated with Crohn's disease (20).
- Inflammation in ulcerative colitis is limited to the rectum and colon. Both Crohn's disease and pouchitis can also cause inflammation in the small intestine e.g. ileum (21).
- On an immunological level, Crohn's disease is Th1-mediated, while ulcerative colitis is mostly Th2-cytokine driven. Pouchitis seems to be Th1-mediated like Crohn's disease (22,23).

The focus of our study is on the pathogenesis and treatment of pouchitis and the transition from the environmental to the immunological side. This includes bacterial dysbiosis and the compromised intestinal mucosal barrier. In theory, an imbalance of the gut microbiome in the gastrointestinal tract results in an incorrect response of the immune system to bacteria (24). In a healthy individual, macrophages clear away invading microbes without the need to raise a specific immune response (25,26). When the immune system has to be activated, macrophages and dendritic cells act as sensing and APC (Antigen-presenting cells) to create an adequate response (27). DC (Dendritic cells), the connection between the innate and the adaptive immune system, accumulate in the mucosa of patients with IBD (28). When an immature dendritic cell digests a microbe after recognizing it as pathogenic through PRR (pattern recognition receptors), the pathogen is degraded into fragments and presented at the cell surface. The mature cell then migrates to a lymph node where it can activate T-helper cells, T-killer cells and B-cells to create an immune response. Dendritic cells can also induce T-cell tolerance. To determine if an antigen is to be tolerated or whether further activation of the immune system is necessary, a special type of PRR is used, called a CLR (C-type lectin receptor). CLR on the surface of dendritic cells can either induce or repress the production of various inflammatory cytokines or chemokines (29).

An essential step in the pathogenesis of Crohn's disease is an inappropriate activation of the immune response likely due to dendritic cells and signaling between PRR and CLR.

Bacteria have been suggested to be involved in the pathogenesis of pouchitis, in that areas of inflammation are found to have a high concentration of certain bacteria (19).

Existing treatment in IBD and pouchitis focuses on either the bacterial side, such as antibiotics and probiotics, or the immunological side with the use of immunomodulators, biologicals and glucocorticoids.

Our study attempts to target the conversion of the bacterial to the immunological side, where dendritic cells are involved while also targeting the bacterial imbalance. These dendritic cells present the broken-down bacteria to the immune system, which reacts incorrectly and creates inflammation.

